3.5 Statistical interim analyses and stopping guidance

No interim analyses were planned in this study. The study's duration has been specified to last during the winter months of 2020–2021, with a duration from 1–6+ months for the participants.

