6.1 Outcome definitions

Primary variables:

- First primary: Serious COVID-19 (MSIS-confirmed COVID-19 with dyspnoea, hospitalisation, or death)
- Second primary: COVID-19 defined by positive PCR obtained from MSIS
- Third primary: A negative SARS-CoV-2 test (MSIS).
- Fourth primary: Self-reported airways infection

The first incidence of report of any of the above primary variables will be used in the analyses. The specified order will be used for the fallback analyses. The values of all variables will be Yes/No to the condition together with time from one week after start of oil consumption to first reporting of the condition, i.e. Yes (except for third primary variable, where total number of negative tests is reported). Those not reporting a Yes answer, the last reported time will be used as censoring time. The date from one week after oil-consumption starts to the date of reporting of a Yes will be converted to number of days from the first to the second date.

The primary analysis set is the defined ITT sample with missing data on outcome counting as the negative outcome.

Compliance

For sensitivity analyses on compliance, we will define compliant participants as those having taken CLO for at least 2 months. We will also analyse participants based on volume CLO taken (more than 250 ml).

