6.2 Analysis methods

The first, second and fourth primary variables will be analysed for relative risk (risk ratio) of acquiring a condition using cod liver oil versus corn oil using the Wald test³. Time to first occurrence of the primary variables will be plotted using the Kaplan-Meier approach. The third primary variable will be compared for the two treatment groups tested using study duration-adjusted counts. If the use of student's t-test cannot be used due to underlying assumptions not holding up, a median test will be used. If appropriate, the Cox proportional hazard regression will be used to assess the effect of the outcome of the above specified baseline variables on time to occurrence of the primary variables. Otherwise, logistic regression on the occurrence of outcome will be undertaken with the same explanatory variables. The explanatory variables to be included in the main regression analyses are:

- Age at CLOC screening
- Gender
- BMI

³ © SAS Institute Inc. https://documentation.sas.com/doc/no/pgmsascdc/v_016/statug/statug_freq_details70.htm, 18-Aug-2021

- Occupational status (employed/not employed?)
- Children at home (Y/N)
- Chronic disease (Y/N ≥ 1 chronic diseases)
- Dietary intake (Y/N)
 - Cod liver oil
 - Vitamin D
 - Omega 3
 - Fish consumers
- Present smoker (Y/N)

Other variables will be included in ad hoc/exploratory analyses.

The sample size in this study is so large that normal assumptions are likely to be valid. If this should not be appropriate for specific variables, appropriate non-parametric alternatives will be used. Should the assumptions to use Cox proportional hazard model not be satisfied, an alternative approach is logistic regression. The assumptions for methods used will be assessed. Should they be violated and not rectified by the sample size, alternative approaches will be used.

Sensitivity analyses will be conducted by including subsets of the study sample based on compliance. Other baseline variables may also be proposed as basis for ad hoc sensitivity analyses. Overdispersion will be considered for models where that can be an issue.

Further ad hoc subgroup analyses may be performed based on the findings of the primary analyses.

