Under the current pandemic with thousands of deaths daily worldwide, there is an urgent need to rapidly identify possibly safe and efficient preventive measures against Covid-19 and the complications of the disease. The study is designed to obtain such evidence in a timely manner without exposing the participants to unnecessary risk.

Justification for Dose

The most commonly used daily dose of cod liver oil is 5 ml and this dose will also be used in the study. This dose has been shown to increase the vitamin D levels of volunteers significantly, and contains the daily requirement of vitamin D in for most adults in Norway.

End of Study Definition

The End of study is defined as the last day of cod liver oil taking in the spring of 2021. (Participants will still be followed after this date.)

5. Study population

Inclusion criteria

Any person >18 years with a Norwegian Personal Identity Number

Exclusion criteria

An electronic questionnaire will be used to collect self-reported data about exclusion criteria.

- History of renal failure or dialysis, hypercalcaemia, severe liver disease (chirrosis), sarcoidosis or other granulomataous disease (Wegener)
- Allergy to fish or corn oil.
- Pregnancy or planned pregnancy before summer 2021
- Vegan diet
- Age >75 years old at inclusion based on the Norwegian Personal Identity Number
- Difficulty of swallowing cod liver oil or other oils
- Previous Covid-19 disease
- For Caucasians only: Use of any supplement containing more than trace amounts of vitamin D or omega-3 fatty acids at inclusion (Vitamin D levels in non-Caucasians living in Norway are frequently low even among those self-reporting using dietary supplements).

 This criteria will be relaxed if too few participants volunteers to the study and only Caucasians that use cod liver oil or an equivalent dietary supplement (with vitamin D) more than 5-7 times per week will be excluded. Furthermore, Caucasians that use supplements with omega-3 fatty acids will not be excluded.

Lifestyle Considerations

No restrictions are required

Recruitment

A large number of participants must be recruited in a short period of time. The following recruitment strategies will be employed:

- 1. The CLOC invitation letter and screening questionnaire will be sent to Koronastudien participants.

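### The Cox regressions in SAP 6.2 have no calendar-time or start-date term, so hazard ratios for baseline covariates related to start date can be distorted; the randomised comparison is not affected

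*SAP*

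**What the plan says.** **Time scale.** SAP 6.1 records each yes/no outcome "together with time from one week after start of oil consumption to first reporting of the condition". It adds: "The date from one week after oil-consumption starts to the date of reporting of a Yes will be converted to number of days". For the rest, "Those not reporting a Yes answer, the last reported time will be used as censoring time". SAP Appendix 1 closes the outcome windows on 2 June 2021 for everyone.

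**Model.** SAP 6.2 states the purpose of the time-to-event model: "Cox proportional hazard regression will be used to assess the effect of the outcome of the above specified baseline variables on time to occurrence". It then gives a closed list under "The explanatory variables to be included in the main regression analyses are": age, gender, BMI, occupation, children at home, chronic disease, four dietary items (cod liver oil, vitamin D, omega-3, fish) and smoking. Start date, calendar period and strata are absent. The only opening is "Other variables will be included in ad hoc/exploratory analyses". If Cox is not appropriate, logistic regression with the same variables replaces it.

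**Staggering.** SAP 3.5 describes the study as running "with a duration from 1–6+ months for the participants".

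**Supplement users.** Protocol section 5 excludes Caucasians who use vitamin D or omega-3 supplements, then says: "This criteria will be relaxed if too few participants volunteers to the study". SAP 3.2 admits Caucasians using such supplements on fewer than 5 days per week, without a condition or date, and dark-skinned participants whatever their previous use.

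**Status.** SAP 4.1 calls the regressions supplementary and keeps them outside the fallback procedure. Protocol section 9 (Analysis sets) names Cox regression among the methods for the primary endpoints.

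**The concern.** On a time-since-own-start axis, each risk set compares people at the same day on study but at different calendar dates, and late study days come only from early starters. SAP 3.3 itself says that power depends heavily on COVID-19 incidence and provides for the situation to change. If a covariate becomes more or less common as recruitment proceeds, its hazard ratio can absorb part of the difference in incidence between early and late starters.

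The covariates most open to this are prior cod liver oil, vitamin D and omega-3 use, because the supplement exclusion could be relaxed after a recruitment shortfall. At stake is a null association with prior use appearing as mildly protective or harmful in the report of a randomised trial. The trial's own efficacy answer is not at stake.

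**Working it through.** The plan gives no figure to reproduce here, no distribution of start dates and no incidence curve. The check is therefore a set of labelled scenarios.

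**1. How far apart can starts be?** Counting back from 2 June 2021, 6 months gives about 2 December 2020 and 1 month gives about 2 May 2021, a spread of 151 days. Short durations may partly be early stopping, and the protocol schedule planned inclusion for September-October 2020. I therefore used spreads of 30, 90 and 150 days.

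**2. Formula.** For a binary covariate x, rare events and true hazard ratio 1, the large-sample Cox estimate solves

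Σ_t { E1(t) − [E1(t) + E0(t)] · R1(t)e^β / [R1(t)e^β + R0(t)] } = 0

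with R_x(t) = Σ_s w_x(s) and E_x(t) = Σ_s w_x(s)·h(s + 7 + t). Both sums run over start days s with s + 7 + t no later than the close. Here w_x(s) is the share of participants with covariate x starting on day s, and h is the hazard by calendar day.

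**3. Gradual change in hazard.** Assumed: first start about 10 November 2020 (close at day 204), uniform starts, hazard rising or falling linearly 2- or 4-fold, or peaking in mid-March. Covariate prevalence is constant at 30%, or moves from 20% to 40% (moderate) or 10% to 60% (strong) over start dates.

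| Spread of starts | No link | Moderate | Strong |
|---|---|---|---|
| 30 days | 1.00 | 0.99-1.01 | 0.97-1.03 |
| 90 days | 1.00 | 0.96-1.03 | 0.90-1.08 |
| 150 days | 1.00 | 0.94-1.04 | 0.86-1.11 |

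**4. One step in the hazard.** Assumed: first start 1 November 2020 (close at day 213), 150-day spread, hazard changing once at day 106 (mid-February).

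| Later/earlier hazard | Moderate | Strong |
|---|---|---|
| 0.5 | 0.95 | 0.88 |
| 2 | 1.04 | 1.10 |
| 3 | 1.06 | 1.14 |

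A steeper fall, to one third, gives 0.91 and 0.80. That is the edge of what gradual drift produced in these runs.

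**5. All users shifted as a block.** Same step, hazard doubled, 25% users, each group starting uniformly over 90 days. Shifts of 30, 60 and 90 days give 1.13, 1.27 and 1.44. The two groups then share 60, 30 and essentially none of their 90 intake days.

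**6. After the fix.** On a calendar time scale the null hazard ratio is 1.00 in every gradual-hazard scenario of step 3 (run with strong drift). This follows because the hazard was assumed to depend on calendar date only. Stratifying by 30-day block of start gives 0.99-1.01 for the strong-drift scenarios with 90- or 150-day spread in steps 3 and 4, and 1.00 for the 60-day shift in step 5. If nearly all starts fall in one block, stratification changes little (0.97-1.03), but the bias is then small anyway.

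**7. The logistic alternative.** It ignores follow-up length as well. Take a constant hazard, 150-day spread and strong drift, so p(s) = 0.1 + 0.5s/150 with mean 0.35, and follow-up 204 − 7 − s = 197 − s.

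- Mean start day, users: (0.1×75 + 0.5×7525/150)/0.35 = 32.58/0.35 = 93.1, so follow-up is 103.9 days.
- Mean start day, non-users: (75 − 32.58)/0.65 = 65.3, so follow-up is 131.7 days.
- Null odds ratio for a rare outcome: about 103.9/131.7 = 0.79, with no change in incidence at all.

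**The case against.** The strongest reply is that nothing confirmatory depends on these models. Endpoints 1, 2 and 4 are tested by Wald risk ratios between randomised arms, and the third by a comparison of counts. Allocation is 1:1 and concealed, so arm corresponds to the no-link column. The objectives concern randomised intake, not prior use. Time since start of intervention is also a natural scale for a trial. All of this stands, and it makes the point minor.

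Three stronger readings are tempting, and the documents do not support them.

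- **That the covariate hazard ratios are mixed with joining era.** This needs a link between covariate and start date. The relaxation is conditional and undated, SAP 3.2 attaches no timing to it, and dark-skinned users could enter from the outset. The link is possible, not shown.
- **That the bias rivals the Koronastudien odds ratio of 0.8.** In these runs that takes a block shift of users with little overlap in start dates, or the most extreme drift combined with a hazard falling to one third. The benchmark is also weak: Caucasians who use such supplements nearly daily are excluded, so the covariate is not the Koronastudien exposure.
- **That the mixing will force the switch to logistic regression.** It could produce apparent non-proportionality, but nothing here quantifies that, and SAP 6.2 already commits to checking assumptions.

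**Conclusion.** The point holds as a conditional, minor weakness in the supplementary regressions. The time origin and the missing calendar term are on the page. Staggered starts are a sound inference from the 1 to 6+ months and the common close. A link between prior supplement use and start date is plausible but undocumented.

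Under the assumptions shown, a true hazard ratio of 1 becomes about 0.95-1.06 with moderate drift and 0.88-1.14 with strong drift when the hazard halves, doubles or triples in one step over a 150-day intake. Gradual changes in hazard give similar ranges (0.94-1.04 and 0.86-1.11). With no link it is 1.00. Larger values, such as 1.27, need most users to start after most non-users, apart from the steep-fall case above. A reader might infer that the trial's efficacy results are biased; they are not biased by this.

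**What to change.** In SAP 6.2, add one sentence. Either stratify the Cox baseline hazard by calendar month of oil start, taken from deriv_Date_CLO_start_corr, or use calendar date as the time scale with delayed entry one week after oil start. Check proportional hazards in that model. If the logistic alternative is used, include month of oil start as a term; with a common close this also absorbs most of the difference in follow-up length.

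The calendar scale is the more complete of the two if starts cluster within a month or so. Tabulating start dates by prior supplement use would show whether the issue arises at all.

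The cost is one line of SAS code, one more stratification factor and a trivial loss of precision. The start date is already held and already defines the time origin, so no new data are needed. The risk ratios and the fallback tests stay as written.

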6.3 Missing data

The primary variables will be assumed to be negative, A “No” answer, if no positive answer is reported.

6.4 Harms

Adverse events will be presented for each treatment group, at each reporting time and accumulated over the whole study duration from start of oil consumption.

Data will be summarized in tables of means and medians for continuous variables and tables of counts for discrete variables. Sufficient detail on summarizing safety data, e.g., information on severity, expectedness, and causality; details of how adverse events are coded or categorized; how adverse event data will be analysed, i.e., grade 3/4 only, incidence case analysis, intervention emergent analysis

6.5 Statistical software

SAS[®] version 9.4 will be used to analyse the data.

Appendix 1: SAS variable names used in the received data set

The table below presents the SAS variable names as they appear in the original SAS data set received.

Variables	SAS variable names
Age group	
Gender	
Weight	
Height	
BMI	
Occupational status	
Education level	
Household income	
Household count	
Children living at home	
Smoking habits	
Chronic disease (Yes/No)	
Parents ethnic origin	
Skin type	
Sun exposure (July to October 2020)	
Dietary intake (Yes/No):	
Vitamin D supplement	
Omega-3 supplement	
Cod liver oil	
Fatty fish intake	
Compliance	
Airways infections	
SARS-CoV-2-tested	
Self-reported free-text side effects	
Laboratory measurements:	
Vitamin D	
Omega-3 index	
Baseline serology	

Primary variables:	
1. Serious COVID-19 (MSIS-confirmed COVID-19 with Dyspnoea, hospitalisation, or death)	CLOC_primary_1_severe_c19
2. COVID-19 defined by positive PCR obtained from MSIS	CLOC_primary_2_msis_status
3. A negative MSIS SARS-CoV-2 test	CLOC_primary_3_negative_tests
4. Self-reported airways infection	CLOC_primary_4_selfrep_airway

Description of the calculation of the four primary variables

- **First primary:** Serious COVID

- *CLOC_primary_1_severe_c19*

- Created by merging *deriv_sym_dyspnea_post_cov_yn_ever* and *deriv_hosp_post_cov_yn_ever* (see description below).
 - 1 = ever answered yes for dysp or hosp
 - 0 = only answered no for dysp or hosp
 - 999 = has filled out forms, has not answered for dysp or hosp question
 - NA = has not filled out forms / not tested positive (second primary)

- Only participants fulfilling the criteria for the second primary, will be included in this analysis. In addition, participants who have tested positive within one week after start of oil consumption are excluded from the analysis (*exclude_Msis_transtart7d*).

- Dyspnoea criteria

- Variable: *deriv_sym_dyspnea_post_cov_yn_ever*

- Answered dyspnoea in forms (R1-R6, E2, Q1) submitted after positive cov test (MSIS)
 - 1 = ever answered yes in any form
 - 0 = only answered no in any form
 - 999 = has filled out form, has not answered dypnoea question
 - NA = has not filled out form

- Hospitalized criteria

- Variable: *deriv_hosp_post_cov_yn_ever*

- Answered hospitalized because of COVID in forms (B1, B2, R1-R6, E2) submitted after positive cov test (MSIS)
 - 1 = ever answered yes in any form
 - 0 = only answered no in any form
 - 999 = has filled out form, has not answered hospitalized question
 - NA = has not filled out form

- Death criteria

- Participant registered as dead/deceased in the National Population Register after a positive cov test (MSIS), but only if the death was related to COVID-19 based on hospital records or information from relatives.

- **Second primary:** New MSIS positive

- *CLOC_primary_2_msis_status*
 - Created from *MSIS_CLOC_test_status*
 - 1 = tested positive for the first time during **CLOC participation period**
 - 2 = only tested negative during **CLOC participation period** (never positive)
 - 3 = untested during **CLOC participation period** (never positive)
- Participants who have tested positive within one week after start of oil consumption are excluded from the analysis (*exclude_Msis_transtart7d*).
- MSIS criteria
 - Variable: *MSIS_CLOC_test_status*
 - 1 = tested positive for the first time during CLOC
 - 2 = only tested neg during CLOC (never positive)
 - *Variables obtained through MSIS (translated): “Test date” and “Test result”*
 - Variable to be analyzed as second primary endpoint identifying only tests registered during the **CLOC participation period** (defined as period from start of cod liver oil/placebo consumption (*deriv_Date_CLO_start_corr*) to June 2, 2021).
- **Third primary: Negative test**
 - *CLOC_primary_3_negative_tests*
 - Generated from *MSIS_CLOC_TotalTests_7d_neg*
 - Sum of total negative tests registered during the period from one week after start of cod liver oil/placebo consumption (*deriv_Date_CLO_start_corr*) to June 2, 2021.
 - 0 if no tests registered
 - Negative test criteria
 - Variable: *MSIS_CLOC_TotalTests_7d_neg*
 - Sum of total negative tests registered during the period from one week after start of cod liver oil/placebo consumption (*deriv_Date_CLO_start_corr*) to June 2, 2021.
 - Supplementary variables
 - *MSIS_CLOC_FirstNegative*
 - Date of first negative test registered during the **CLOC participation period**.
 - *MSIS_CLOC_LastNegative*
 - Date of last negative test registered during the **CLOC participation period**.
- **Forth primary: Self-reported airway infections**
 - *CLOC_primary_4_selfrep_airway*
 - Generated from *deriv_respinf_date_yn*
 - 1 = ever answered yes and provided valid date in any form
 - 0 = only answered no, or provided non-valid date in any form
 - 999 = has filled out form, has not answered airway infections question
 - NA = has not filled out form
 - Any self-reported airway infections during the period from one week after start of cod liver oil/placebo consumption (*deriv_Date_CLO_start_corr*) to June 2, 2021.
 - Self-reported airway infections criteria
 - Variable: *deriv_respinf_date_yn*

- Answered question *has had respiratory infection since last cloc report* in any CLOC questionnaire (R1-R6)
 - *deriv_respinf_report_yn_ever*
- Date of self-reported airway infections in the period from one week after start of cod liver oil/placebo consumption (*deriv_Date_CLO_start_corr*) to June 2, 2021.
 - *deriv_respinf_date_sums*
-
- Supplementary variable
 - *deriv_respinf_count_report_sum*
 - Number of respiratory infections reported
 - *Rx_Date_respiratoryinfectionx_sym_start_report*
 - Date of each infection reported in each report form

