3.3 Sample size

The fallback method (<https://www.fda.gov/media/102657/download>) will be used to correct for testing of multiple primary endpoints.

The total alpha (0.05) will be divided among the endpoints, and a fixed sequence for the testing will be maintained. As the testing sequence progresses, a successful test preserves its assigned alpha as "saved" (unused) alpha that is passed along to the next

test in the sequence. This passed-along alpha is added to the assigned alpha of the next endpoint, and the summed alpha is used for testing that endpoint. Thus, as sequential tests are successful, the alpha accumulates for the endpoints later in the sequence; these endpoints are then tested with progressively larger alphas.

Endpoints in testing order with power calculation:

1. Serious COVID-19 (MSIS-confirmed COVID-19 with dyspnoea, hospitalization, or death). (MSIS: Mandatory Norwegian Surveillance System for Communicable Diseases). Assigned $\alpha=0.018$.

Based on the observations in Koronastudien of a 40% reduction in serious COVID-19 in the group reporting use of cod liver oil, and an expected incidence of 0.25%, a power of 70%, 67,000 participants will have to be included for this endpoint.

2. COVID-19 positive PCR (MSIS). Assigned $\alpha=0.03$.

Based on the observations in Koronastudien of a 20% reduction in COVID-19 incidence in the group reporting use of cod liver oil, and an expected incidence of 1%, a power of 70%, 65,000 participants will have to be included for this endpoint.

3. A negative SARS-CoV-2 test (MSIS). Assigned $\alpha=0.001$.

COVID tests (SARS-CoV2-2), real time (RT)-PCR, are mostly obtained because of a suspicion of COVID-19. The number of negative COVID tests from one week after starting taking cod liver oil/placebo and to the end of the intervention period. This endpoint has been added as an alternative to the Positive PCR or bacterial culture endpoint (now a secondary endpoint, as it is not available at this time).

4. Self-reported airway infection. Assigned $\alpha=0.001$.

Based on the expected frequency of airway infections in Koronastudien of >30% and as a threshold of clinically interesting reduction of all airway infections of 10%, 23,000 participants will have to be included for this endpoint. The study has a power for this endpoint >95%. 16,000 participants in the study will give an 80% power for this endpoint.

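### SAP Appendix 1 derives serious COVID-19 from dyspnoea and hospitalisation only; death, a stated component, has no variable, no code and no place in the merge

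*SAP*

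**What the plan says.** **Definition.** SAP 3.3 gives the first endpoint in the testing order as "Serious COVID-19 (MSIS-confirmed COVID-19 with dyspnoea, hospitalization, or death". SAP 6.1 repeats it: "First primary: Serious COVID-19 (MSIS-confirmed COVID-19 with dyspnoea, hospitalisation, or death". The Appendix 1 table attaches the same wording to `CLOC_primary_1_severe_c19`: "Serious COVID-19 (MSIS-confirmed COVID-19 with Dyspnoea, hospitalisation, or death". Protocol section 3 (endpoint A, item C) and the sample size text in protocol section 9 also include death.

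**Derivation.** Below that table, Appendix 1 says how the variable is built: "Created by merging *deriv_sym_dyspnea_post_cov_yn_ever* and *deriv_hosp_post_cov_yn_ever* (see description below". The event code is "1 = ever answered yes for dysp or hosp". Codes 0 and 999 likewise refer only to the dyspnoea and hospitalisation questions. NA covers participants who returned no forms or did not test positive.

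**Death entry.** Further down, under the same endpoint, a death criterion relies on the National Population Register after a positive test, "but only if the death was related to COVID-19 based on hospital records or information from relatives". The dyspnoea and hospitalisation criteria each have a variable name and a 1/0/999/NA code list. The death criterion has neither.

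**Missing data.** SAP 6.1 states: "The primary analysis set is the defined ITT sample with missing data on outcome counting as the negative outcome". SAP 6.3 likewise treats the absence of a positive answer as No.

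**The concern.** The derivation and the definition disagree about which participants have the event. Both coded components need a questionnaire returned after the positive test. A participant who dies may never return one, so the cases most clearly serious are among those most exposed to being coded as missing and then counted as non-events.

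This is the first test in the fallback sequence, at alpha 0.018, and its result decides whether the second endpoint is tested at 0.03 or at 0.018 + 0.03 = 0.048. Two programmers could build different variables, one from the code list and one from the criteria, and each could claim to follow the SAP. Left open, the choice would be made during analysis.

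There is also a mismatch of sources. The death entry accepts hospital records or relatives as evidence that COVID-19 was responsible. Protocol section 3 accepts the death certificate as well. A death attributable by certificate alone meets the protocol endpoint but not the Appendix 1 criterion.

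**Working it through.** **1. Tracing a COVID-19 death through the written codes** (first positive MSIS test more than one week after starting oil, then death from COVID-19)

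| Forms returned after the positive test | Code as written | After SAP 6.1/6.3 | By the definition |
|---|---|---|---|
| A Yes to dyspnoea or hospitalisation | 1 | Event | Event |
| Only No answers | 0 | Non-event | Event |
| Form returned, questions not answered | 999 | Non-event | Event |
| No form returned | NA | Non-event | Event |

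The definition and the code agree only in the first row. Deaths preceded by a Yes are unaffected; the gap concerns the other three rows.

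**2. Reproducing the planned sample size**

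Inputs from SAP 3.3: incidence 0.25%, 40% reduction, alpha 0.018, power 70%, N = 67,000, allocation 1:1. I take 0.25% as the placebo rate, so p1 = 0.0025 and p2 = 0.6 × 0.0025 = 0.0015, and the test as two-sided (the SAP does not say).

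The two-proportion formula with pooled variance under the null, mean rate p = 0.0020, is

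n per arm = [z(0.991)·√(2p(1−p)) + z(0.70)·√(p1(1−p1) + p2(1−p2))]² / (p1 − p2)²

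With z(0.991) = 2.3656 and z(0.70) = 0.5244, this gives 33,342 per arm, or 66,684 in total, against 67,000 stated. The plan's figure reproduces. It already refers to the composite with death, so correcting the code does not change it.

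**3. What the gap could cost**

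The documents do not split serious events by component. As an assumption, let a share d of serious events in each arm qualify by death alone, with d = 1% to 5%. SAP 6.2 names a Wald test of the risk ratio, so power is taken on the log risk ratio:

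Var = (1−p1)/(n·p1) + (1−p2)/(n·p2); power = Φ(|ln 0.6|/√Var − 2.3656), with |ln 0.6| = 0.5108

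Both rates are multiplied by (1 − d). The ratio stays 0.6 because the factor cancels.

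At n = 33,500 per arm (67,000):

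| d | Events, placebo + oil | √Var | 0.5108/√Var | Power |
|---|---|---|---|---|
| 0 | 83.75 + 50.25 = 134 | 0.1783 | 2.865 | 69.1% |
| 1% | 82.91 + 49.75 = 132.7 | 0.1792 | 2.851 | 68.6% |
| 5% | 79.56 + 47.74 = 127.3 | 0.1829 | 2.793 | 66.5% |

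Between 1.3 and 6.7 of 134 events would be lost. At the recruitment aim of 80,000 (160 planned events), the same steps give 77.8% falling to 77.3% and 75.4%.

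These figures put all planned participants in the denominator. SAP 4.2 defines the ITT set more narrowly, leaving out people whose shipments were returned, so the analysed number would be somewhat lower.

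**The case against.** The strongest reply is that the intention is clear. Death appears in every definition and in the label of the very variable being built. The merge line points to descriptions below it, and three criteria follow, death among them. Protocol section 8 also treats COVID-19 deaths as key endpoints: they are validated against hospital or GP records, read again by an independent blinded physician and, where the two disagree, sent to a blinded committee. A verified death is therefore unlikely to go unnoticed.

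Most of this stands. A reader might infer that the SAP dropped death from the endpoint. The death criterion listed under the same primary contradicts that; this is a gap in the derivation. But intention and validation do not supply the missing code. The merge names two variables, the event code names two answers, and nothing says where the adjudicated death enters.

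The reply also qualifies the point about sources. Because section 8 validates registry deaths against records, Appendix 1's reliance on hospital records is partly in line with the protocol. The task is to reconcile three passages, protocol sections 3 and 8 and Appendix 1, and not simply to add the certificate.

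Two other stronger readings are not supported:

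- **Late dyspnoea.** Appendix 1 counts a Yes at any time in a listed form submitted after the test, while protocol section 3 asks for dyspnoea and hospitalisation at the time of the positive test. A reader might infer that unrelated late symptoms inflate the endpoint. That depends on questionnaire wording the documents do not contain, and the hospitalisation item already asks about admission because of COVID-19. It is a wording conflict with no effect shown.
- **Denominator.** Appendix 1 also says "Only participants fulfilling the criteria for the second primary, will be included in this analysis". Whether that restricts the analysis to test-positive participants is a separate question, and any power loss from it should not be charged to the death gap.

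**Conclusion.** The point holds as a derivation gap that should be fixed. As written, the coding can score a COVID-19 death as no serious COVID-19, against the endpoint's own definition, and the missing-data rule makes that outcome final.

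The size is probably small and cannot be established from the documents. On the assumed 1% to 5% death-only share, equal in both arms, the power loss at 67,000 is 0.5 to 2.6 percentage points. A reader might infer a biased risk ratio, but with an equal share in both arms the ratio is unchanged, and the documents give no ground for assuming unequal shares. The calculation also rests on 0.25% being the placebo rate, a two-sided test, and all planned participants in the denominator.

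The case for correction therefore rests on having one unambiguous definition of the first-tested endpoint, more than on power.

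**What to change.** Before unblinding, in SAP Appendix 1:

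1. Add a named death variable with its own code list.
2. Set `CLOC_primary_1_severe_c19` to 1 if death, dyspnoea or hospitalisation is met, with a Yes on any component overriding 0, 999 or NA on the others.
3. State which evidence establishes that a death was related to COVID-19, reconciled with protocol section 3 (which includes the death certificate) and with the record validation in protocol section 8.
4. As a minor item, reconcile the wording on timing between Appendix 1 and protocol section 3, and say which forms or questions count as concurrent. A form's submission date is not the symptom date, so the rule should not drop a form returned late that describes the test episode.

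The cost is SAP wording, one variable and one line of recoding. Cause-of-death data are already on the protocol's registry list, and the record review needed to judge relatedness is already planned in section 8. Sample size and alpha do not change. SAP 3.3 and protocol section 9 both allow changes to the statistical analyses before unblinding.
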